1. RISKS TO THE SUBJECTS

a. Human Subjects Involvement and Characteristics

1. The subject will complete safety screening including presence of any metal in the body, history of epilepsy, and concussion.
2. The level of hand and arm movement as well as fingers' touch sensation will be assessed. For movement assessment, the subject will be asked to move the hand and arm in specific ways as best as one can and move objects in different sizes and shapes around the table with the hand as quickly as possible. For sensation assessment, the subject will be asked if s/he can feel a small touch on fingertips.
3. If the subject is eligible for the study, the subject will be randomly assigned to one of two groups. This means that the subject has a 50/50 chance (like flipping a coin) of being in either group. Neither the researchers nor the subject will make the choice of which group to which the subject is assigned. The two groups are Group A (unperceivable wrist vibration group) and Group B (placebo, no wrist vibration group).
4. For both groups, we will ask the subject about the stroke type (ischemic or hemorrhagic) and location as much as the subject knows.

5. For both groups, we will perform four types of evaluations to measure recovery. The assessment of the hand/arm movement ability and finger sensation will serve as evaluation #1 (clinical hand function). Evaluation #1 may take an hour.
6. In addition, the subject will have a Magnetic Resonance Imaging (MRI) exam (evaluation #2). This MRI exam includes an anatomical scan to specify the area of the brain that we will stimulate using transcranial magnetic stimulation (TMS) for the next evaluation, DKI that provides information about the architecture within the cortex relevant to revealing lesion-specific impairment, and fMRI to examine brain networks used during hand grip. For the MRI exam, the subject will lie down on a narrow bed which will then be placed in a tunnel that is 6 feet by 22 inches wide and open at each end. the subject will lie there quietly for about half an hour, during which time the subject will hear a loud noise. The subject may feel warm during this procedure. Evaluation #2 will take approximately an hour.
7. Next, excitability of neurons in the brain will be assessed using TMS (evaluation #3, TMS). TMS is a noninvasive brain stimulation device. We will help the subject put an elastic cap onto the head. This cap is like a swimmers cap. The subject will be asked to sit in a cushioned chair and asked to be at rest or hold a light grip while the brain receives stimulation. A TMS pad will be held above the head. The tester will trigger a switch on the TMS paddle which will deliver a magnetic pulse to the outside of the skull. The subject will hear a clicking sound when the paddle produces its magnetic energy and the subject might feel a light tap against the scalp. The magnetic pulse stimulates the brain nerves controlling the hand. Therefore the subject may or may not feel the hand muscle briefly twitch depending on the strength of the TMS pulse. The subject might also feel the facial muscles twitch slightly just around the eye. This twitch is a result of the TMS directly stimulating the facial nerves and muscles that run directly under the scalp. The TMS pad may be moved around the head until the best position is located to give a contraction of the hand muscle. This contraction will be measured by a muscle activity sensor that will be placed on the hand skin with a sticky pad and/or tape. Evaluation #3 may take a half an hour.
8. For the fourth evaluation, the subject will wear a cap weaved with electrodes on the head. The electrodes will have gels on them and the gels can make hair messy. So the subject may be advised to bring a hat to wear after this session. The subject will be seated and either receive light touches on the fingertip at rest or pinch at a light force (as in holding a pen) upon cues, while brain activity is recorded using the electrodes of electroencephalogram, EEG (evaluation #4, EEG). Evaluation #4 may take two hours.
9. After completing all evaluations, both groups will receive upper limb therapy 3 times a week for 2 consecutive weeks (for a total of 6 sessions) while wearing a vibrator at the wrist. An off-the-shelf mechanical vibrator in the size of a dime will be used. During therapy, Group A will receive vibration at the wrist at the level that is imperceptible. Group B will receive placebo, also in zero vibration at the wrist, during therapy. Both groups will not feel any vibration at the wrist during therapy, because the vibration is either very small or none. The therapy will focus on object manipulation, dexterous hand movement, and coordinated hand and arm movements.
10. After the last therapy session, all four evaluations (hand clinical function, MRI, TMS, and EEG) will be performed again.
11. Two weeks after the last therapy session, the subject will come to MUSC again to go through the three evaluations again (hand clinical function, TMS, and EEG).

Thirty chronic stroke survivors will be recruited (with 15 in each of the control and experimental groups). The age range will be 21 and older.

The inclusion criteria are mild to moderate impairment in upper extremity function (approximately 30 to 60 on the Fugl-Meyer Upper Extremity without the reflex portion). Exclusion criteria are cognitive dysfunction as evidenced by inability to follow three-step instructions and/or provide consent to participate in the study, stroke<3 months (to avoid interference with acute care), treatment with botox in the affected arm within 3 months of start of study, and age <21. Individuals with MRI contraindications (e.g., metal in the body, claustrophobia, pregnancy) or TMS contraindications (e.g., history of seizure, concussion, pregnancy) may still be considered for the study, but will not complete the contraindicated evaluation. Inclusion is based on clinical assessment, because recovery relates most with initial impairment level, not lesion characteristics.

Targeted/Planned Enrollment Table

Total Planned Enrollment: 30

TARGETED/PLANNED ENROLLMENT: Number of Subjects

Ethnic Category	Sex/Gender		
	Females	Males	Total
Hispanic or Latino	2	2	4
Not Hispanic or Latino	13	13	26
Ethnic Category: Total of All Subjects*	30		
Racial Categories			
American Indian/Alaska Native	0	0	0
Asian	1	1	2
Native Hawaiian or Other Pacific Islander	0	0	0
Black or African American	4	4	8
White	10	10	20
Racial Categories: Total of All Subjects*	15	15	30

Stroke survivors are the target subjects as the intervention under investigation targets to improve rehabilitation outcomes of stroke survivors.

Children are not recruited because stroke is rare in children.

b. Sources of Materials

Recorded data are hand clinical function assessment scores, brain MR imaging data, electromyogram signal data obtained during the TMS session, electroencephalogram signal data obtained during the EEG session, subject characteristic information of gender, age, time since stroke (years and months), stroke type/location (obtained by asking each person), and consent/HIPPA forms. All data are collected specifically for the proposed research project.

All data except the consent/HIPPA forms will be de-identified and labeled by subject codes. The linkage between the subject identities and subject codes will be accessible to the study personnel only.

c. Potential Risks

1. There is a slight risk for loss of confidentiality although researchers will take appropriate steps to protect any information collected about the subjects.
2. Randomization: The treatment one person receives may prove to be less effective or to have more side effects than the other study treatment.
3. Imperceptible vibration: For people in the group that receives vibration at the wrist, prolonged vibration may numb although it is very unlikely because the vibration applied is very small to the extent that it is imperceptible.
4. TMS: TMS could move iron-containing objects in or around the face or head, which could in the process possibly harm the person. There is a slight risk of a seizure with TMS. There is a very low risk of scalp discomfort and headaches. A TMS stimulus may feel like a slight tap to the skull. There may be discomfort from the muscle contraction that occurs in the hand muscle in response to the TMS. There is a very low risk of hearing loss due to the clicking sounds that the TMS machine makes. Safety of TMS in pregnancy is unknown. The use of tape or other adhesives to secure EMG sensors during testing may cause some mild skin irritation.
5. MRI: MRI could move iron-containing objects in the MRI room, which could in the process possibly harm the person. There is discomfort by claustrophobia and by the loud banging noise. Temporary hearing loss has been reported from the loud noise. The person may feel uncomfortable as s/he will be asked not to swallow for a while.
6. EEG: It may be uncomfortable to wear a head cap attached with a bundle of wires during evaluation. Also, the gel used for the electrodes will get hair messy.

7. Unknown Risks: The experimental treatments may have unknown side effects.

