**Medical University of South Carolina
Protocol**

PI Name: [name]

Study Title: Sensory Stimulation to Enhance Hand Function Post Stroke

NCT02675764

TABLE OF CONTENTS

A. SPECIFIC AIMS	2
B. BACKGROUND AND SIGNIFICANCE	2
C. PRELIMINARY STUDIES	2
D. RESEARCH DESIGN AND METHODS	2
E. PROTECTION OF HUMAN SUBJECTS	3
F. REFERENCES/LITERATURE CITATIONS	7
G. FACILITES AVAILABLE	8

A. SPECIFIC AIMS

The objective of this pilot project is to assess the impact of the novel sensory vibration stimulation technique we have developed in enhancing outcomes of hand therapy as well as the central nervous system responsiveness in chronic stroke survivors. This impact will be assessed in a double-blind stratified randomized controlled trial for stroke survivors. The hypothesis is that improvement in hand function will be greater for the experimental group receiving the wrist subthreshold vibrotactile stimulation during therapy compared with the control group who will wear the device with no vibration (placebo), and that this better improvement in hand function is associated with neurophysiologic measures of central nervous system responsiveness.

B. BACKGROUND AND SIGNIFICANCE

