D. RESEARCH DESIGN AND METHODS

The hypotheses will be tested in a double-blind stratified randomized controlled trial. Experimental and control groups will be compared for post-therapy changes in hand function. To obtain two comparable groups, stroke subjects will be stratified by their initial hand motor and sensory scores (Fugl-Meyer and Semmes-Weinstein mild vs. moderate). Subjects will be randomly and blindly assigned to either the experimental or the control group. A standardized task-practice therapy focused on dexterous object manipulation and multi-joint upper extremity coordination will be used, since the intervention targets sensory feedback-based motor control. The research therapists at the SC Stroke Recovery Research Center have been trained in its implementation and routinely use this protocol. Each subject will receive therapy two hours/day, 3 days/week for 2 weeks. The duration of 2 weeks is deemed sufficient to result in statistically greater improvement in motor outcome and cortical reorganization (seen using fMRI/TMS) for the experimental compared to the control group. The two groups will receive therapy of equal intensity individually in the same room supervised by the same therapist who is blinded to the group and does not know how the coin-sized device providing the light vibration works. Tactor (EAI, Casselberry, FL) generating light vibration in our preliminary studies will be applied to the wrist. At the beginning of each therapy session, the subject's sensory threshold will be determined and the vibrating intensity will be adjusted to either 60% of the sensory threshold or zero, depending on the group. Blinding to the light vibration stimulation is possible because subjects cannot perceive subthreshold (imperceptible) vibration, thus they do not know whether they are receiving the vibration or not.

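### The aim names chronic stroke, but the term is undefined beside a 3-month limit set for acute care, and the recorded time since stroke is not used in the strata, the group comparison or the correlations

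*Combined protocol and SAP*

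**What the plan says.** - **Population.** Section A states the objective as "enhancing outcomes of hand therapy as well as the central nervous system responsiveness in chronic stroke survivors". Section E.1.a repeats the label: "Thirty chronic stroke survivors will be recruited (with 15 in each of the control and experimental groups". No section says what *chronic* means in months or years.
- **Time criterion.** The exclusion list in section E.1.a contains "stroke<3 months (to avoid interference with acute care". The other 3-month limit there concerns botulinum toxin treatment, not time since stroke.
- **Basis for inclusion.** The same section says: "Inclusion is based on clinical assessment, because recovery relates most with initial impairment level, not lesion characteristics". This weighs impairment against lesion characteristics and does not mention time.
- **Strata.** Section D: "stroke subjects will be stratified by their initial hand motor and sensory scores (Fugl-Meyer and Semmes-Weinstein mild vs. moderate".
- **Analysis.** The analysis paragraph of section D plans a repeated-measures ANOVA whose test of interest is time by group, and Pearson correlations between hand-function change and the neurophysiologic measures. It names no covariate for either.
- **Data.** Section E.1.b lists "time since stroke (years and months" among the recorded characteristics. It is given no further role.

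**The concern.** Someone just past 3 months meets the written exclusion rule, and that rule was not set to secure a stable baseline. The outcomes are changes over a short interval: two weeks of therapy, then a further two weeks to follow-up (MRI is done only before and after therapy). If change without therapy depends on how recent the stroke is, time since stroke is a prognostic factor for exactly the quantity being analysed. Three things are then at stake:

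1. The reader cannot tell from the criteria which population the result describes.
2. With 15 per arm, the group comparison carries avoidable noise and can be tilted by chance.
3. The second half of the hypothesis in section A links hand improvement to neurophysiologic measures. It rests on correlations across subjects, which randomisation does not protect from a common cause.

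**Working it through.** **Reproduction.** There is no figure in the plan to reproduce. The sample size of 30 comes without alpha, power, effect size or SD.

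**Inputs from the documents.** 30 subjects, 15 per arm (section E.1.a); strata and analysis as in section D.

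**Assumptions, not in the documents.** A share *f* of subjects is early after stroke, and these subjects gain an extra *g* SD of change without therapy, with *g* = 0.5 to 1.0. Allocation is treated as simple 15/15, ignoring the severity strata. Power figures use two-sided alpha 0.05.

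**Step 1: chance imbalance, 6 early subjects of 30.** P(x early in one arm) = C(15,x)·C(15,6−x)/C(30,6), with C(30,6) = 593,775.
- 3:3 split: 455 × 455 / 593,775 = 0.349
- 4:2 split, either way: 2 × 1,365 × 105 / 593,775 = 0.483
- 5:1 or 6:0 split, either way: 1 − 0.349 − 0.483 ≈ 0.17

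With 9 or 12 early subjects, the chance that the arms differ by 4 or more is 11% or 26%. The sequence is uneven because an odd total cannot split with a difference of exactly 4.

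**Step 2: effect of a 5:1 split.** The early share differs by (5 − 1)/15 = 0.267. The shift in the group difference is 0.267 × *g*, which is 0.13 SD for *g* = 0.5 and 0.27 SD for *g* = 1.0. The standard error of a difference with 15 per arm is √(2/15) = 0.37 SD, so the shift is about 0.4 to 0.7 standard errors.

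**Step 3: precision without imbalance.** The SD is inflated by √(1 + f(1−f)g²).

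| f | g | SD factor | Power, if 80% without the mixture |
|---|---|---|---|
| 0.2 | 0.5 | 1.020 | 78% |
| 0.4 | 0.5 | 1.030 | 78% |
| 0.2 | 1.0 | 1.077 | 74% |
| 0.4 | 1.0 | 1.114 | 71% |

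The reference is a true difference of 1.02 SD, which 15 per arm detects with 80% power by the normal approximation.

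**Step 4: correlations.** Suppose early status raises both the hand-function change and the neurophysiologic measure by *g*, with no other link between them. Then r = f(1−f)g² / (1 + f(1−f)g²).
- f = 0.2: r = 0.04 (*g* = 0.5) or 0.14 (*g* = 1.0)
- f = 0.4: r = 0.06 (*g* = 0.5) or 0.19 (*g* = 1.0)

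For comparison, r must reach about 0.36 for two-sided p < 0.05 with 30 subjects.

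**The case against.** The strongest case on the other side has four parts.

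**The main comparison is protected.** Both arms are concurrent, randomised and blinded and receive equal therapy, so recovery without therapy affects both. A reader might infer that the time by group test is biased by natural recovery. It is not, in expectation, and chance imbalance in an unmodelled factor is part of what the test's error rate already covers. This stands. What remains is precision and the credibility of a single small trial.

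**The premise is external.** Nothing in the documents says when stroke becomes chronic, when recovery without therapy ends, or how many entrants will be early. A reader might infer that subjects still recovering naturally will be enrolled, or that a particular later cut-off is required. The text supports neither. Recruitment is through registries and a research directory, and section B describes impairment that has outlasted repeated rehabilitation. These do not bar early entrants, but they give no support to an early share of 20–40% either.

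**Severity is already stratified, and time since stroke is collected.** Stratifying on motor and sensory scores may balance recovery potential in part. It does not make an early and a late subject with the same score equivalent. A reader might also infer that the result could never be stated for chronic stroke. That goes too far, because the time since stroke of those enrolled will be known and can be reported.

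**The sizes are small.** An induced r of at most about 0.19 would seldom reach significance alone, and the correlations serve to identify relevant measures, not to attribute change to vibration. This stands as a limit on severity. It is not a reason to leave a recorded prognostic variable unused.

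**Conclusion.** Two points hold on the text alone. *Chronic* is undefined beside a 3-month limit justified only by acute care, and time since stroke is recorded without any role in the strata or analysis.

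The statistical cost is conditional and modest. It rests on the assumption that subjects nearer to onset change more without therapy, and on assumed values for their share and extra gain. Under those assumptions the group comparison is unbiased in expectation, with some loss of power and a realistic chance of a shift well below the difference of about 1 SD that 15 per arm can detect. The correlations are the weaker part, since nothing in the design separates a shared dependence on time since stroke from a link between hand function and neurophysiology. The induced value also assumes that the neurophysiologic measure shifts as much as the hand score. This is an inexpensive improvement to a pilot, not a flaw that invalidates its main comparison.

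**What to change.** 1. **Reconcile the population and the criterion.** The investigators should define *chronic* and make it agree with the time limit, either in the criterion or in how the population is described. No cut-off is proposed here. Report the distribution of time since stroke by arm.
2. **Group comparison.** Prespecify time since stroke, for example as log months, as a covariate in an analysis of change scores. Alternatively, put it in the repeated-measures model together with its interaction with time. A main effect alone adjusts only the subjects' average level and leaves the time by group test unadjusted.
3. **Correlations.** Report the correlations between hand function and neurophysiology as partial correlations given time since stroke, beside the unadjusted values.

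A third stratification factor is not advised: two binary factors give 4 cells, and a third would give 8, averaging 30/8 = 3.75 subjects.

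**Cost.** No new data are needed. A change-score comparison of 30 subjects goes from 28 to 27 error degrees of freedom, and a correlation loses one likewise. In the three-occasion model, the error degrees of freedom for time by group go from 28 × 2 = 56 to 27 × 2 = 54. If nearly all subjects prove to be late after stroke, the adjustment will gain little.

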2. ADEQUACY OF PROTECTION AGAINST RISKS

a. Recruitment and Informed Consent

Stroke survivors will be recruited from the MUSC stroke research registry database (approved MUSC IRB PRO#15991, [name] PI) at the MUSC College of Health Professions Center for Rehabilitation Research in Neurological Conditions. The database currently contains contact information for ~200 persons with stroke who have signed informed consent to be contacted for research. In addition, the SC Research Directory will be used for recruitment.

Recruitment

This study will recruit from the Registry for Stroke Recovery (RESTORE-Pro#00037803), which is a registry with subjects consented for future contact. RESTORE staff will query the registry for potential subjects and provide the Principal Investigator (PI) with the contact information of subjects who meet their criteria. The PI or research staff will contact subject to further screen for potential enrollment.

Sharing Data

If the subject agrees, the data collected and generated from this study will be shared to the Registry for Stroke Recovery (RESTORE-Pro#00037803) by the subject's registry ID. Sharing data from this study with the registry will allow for more targeted recruitment efforts in the future and allow researchers at MUSC to have a more complete registry with key stroke recovery elements including common data and physical function characteristics that are applicable to multiple studies. MUSC researchers and collaborating facilities will be able to query data sets to learn more about recovery of subjects after their stroke through institutionally managed secure servers that will assure HIPAA privacy and security compliance.

The consent process will take place when the potential participant comes to the laboratory on a scheduled time agreed upon between the study coordinator and the participant. The content of the consent will be verbally explained to the subject and the subject will be asked to raise any questions and concerns. If the person requests a waiting period, then one will be given. If the person desires to consent immediately, then the person will provide consent immediately.

b. Protection against Risk

1. Loss of confidentiality: Appropriate steps will be taken to protect any information collected. The data from test results will be de-identified once it has been collected and before it is stored. This means individual results would not be able to be linked to the subject by others who review the results of this research. The linkage between subject codes and identities as well as all other identifiable information including consent/HIPPA forms will be stored in a locked room and be accessible only to the study personnel.

2. TMS: The MUSC Brain Stim Laboratory requires that all subjects receiving TMS and MRI complete a screening questionnaire to ensure that the person does not have any loose metal objects like earrings or nose rings or a piece of metal in the body such as a fragment in the eye, aneurysm clips, ear implants, spinal nerve stimulators, a pacemaker, or an implant electrical device. A person must be screened before each TMS and/or MRI exam. Persons who do not meet the screening criteria for TMS or MRI may still be considered eligible for the study, but will not complete these evaluations.

The primary safety concern with TMS is the induction of seizures; however, the incidence of seizures is very low and mostly associated with high frequency repetitive TMS (rTMS) which will not be used in this project. Instead we will use single-pulse TMS, which is much safer and we will follow published "gold standard" safety guidelines for diagnostic TMS to minimize the risk of inducing a seizure (*Groppa et al. 2012*).

Hearing protection for all subjects during TMS will be provided. Stimulation sessions will be stopped immediately with any complaints of discomfort or for any complaints of dizziness or light-headedness. There are no lower-risk methods available to gain the same scientific information.

A TMS stimulus may feel like a slight tap on the skull. There is a very low risk of scalp discomfort. The subject will be asked to notify the experimenter if s/he experiences these. The headache or changes in cognitive function is expressed, the subject will stop participating in the study.

Persons with potential for pregnancy will not have the TMS stimulation. Persons with a history of seizures will not have the TMS stimulation.

For mild skin irritation related to the use of tape or other adhesives to secure EMG sensors during testing, the subject will be advised to clean the adhesive residue with either alcohol swab provided or soap and water after the experiment.

5. MRI: The MUSC Brain Stim Laboratory requires that all subjects receiving TMS and MRI complete a screening questionnaire to ensure that the person does not have any loose metal objects like earrings or nose rings or a piece of metal in the body such as a fragment in the eye, aneurysm clips, ear implants, spinal nerve stimulators, a pacemaker, or an implant electrical device. A person must be screened before each TMS and/or MRI exam. To prevent hearing loss, the subject will be asked to wear earplugs. Persons who do not meet the screening criteria for TMS or MRI may still be considered eligible for the study, but will not complete these evaluations.

6. EEG: The gel used for the electrodes can be washed off with shampoo. The subject will be advised to bring a hat to wear for the way home.

7. Unknown Risks: Subjects will be notified if we learn anything that might make them change their mind about participating in the study.

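### Randomise after the baseline evaluations, immediately before therapy session 1: the written order allocates before baseline MRI, TMS and EEG and can lose a randomised person before therapy (minor)

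*Combined protocol and SAP*

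**What the plan says.** **Trigger for randomisation.** Section E.1.a item 3 says: "If the subject is eligible for the study, the subject will be randomly assigned to one of two groups". Section D stratifies on the initial Fugl-Meyer and Semmes-Weinstein scores, so allocation cannot come before the first hand assessment. Section D's list of pre-intervention testing (screening, hand function, MRI, TMS, EEG) does not mention randomisation.

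**Order in the numbered list of Section E.1.a.** Safety screening is item 1, hand assessment item 2 and randomisation item 3. Item 5 introduces four evaluations for both groups. MRI is item 6, TMS item 7 and EEG item 8. Item 9 begins: "After completing all evaluations, both groups will receive upper limb therapy 3 times a week".

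**First use of the allocation.** Section D says that at the start of each therapy session "the vibrating intensity will be adjusted to either 60% of the sensory threshold or zero, depending on the group".

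**Leaving at TMS.** Section E.2.b says: "The headache or changes in cognitive function is expressed, the subject will stop participating in the study". The sentence names no visit. The same section says that a stimulation session is stopped at once for discomfort, dizziness or light-headedness. Section D says that a person who misses an assessment because of scheduling or a safety risk, with a pointer to Section 2.b, forgoes payment for that portion only.

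**Analysis.** Section D plans a repeated measures ANOVA and looks for a time-by-group interaction over three time points. Section E.1.a plans 30 people, 15 per group. No replacement rule, analysis set or missing-data method is given for a person who is randomised but never treated.

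**The concern.** TMS is a measurement in this trial, not the tested treatment. Taken in the written order, allocation happens before MRI, TMS and EEG, and any exit during those evaluations uses up one of 30 allocated places. That person has one of three hand-function time points and none of the six therapy sessions, hence no change score. With 15 per group and stratification, each such loss costs some precision and may upset the balance between groups. It is also avoidable, because nothing in the documents needs the allocation before the first therapy session.

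**Working it through.** **Order of events.** The protocol has no figure of its own to reproduce here: no power, effect size, alpha or dropout rate is stated for the 30. The first check is therefore of sequence.

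| Step | Item in E.1.a | Needs the allocation? |
|---|---|---|
| Hand assessment | 2 | No; it supplies the strata |
| Randomisation | 3 | – |
| MRI, TMS, EEG | 6, 7, 8 | No |
| Therapy | 9 | Yes; sets the vibration |
| Post-therapy evaluations | 10 | – |
| Two-week evaluations | 11 | – |

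An exit at item 7 falls after allocation and before its first use. The hand scores available are 1 of 3 (baseline only).

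**Inputs for size.** From the documents: 15 v 15. Assumed: two-sided 5% test, a two-sample t test on change, and an exit probability p at baseline TMS of 0.5%, 1%, 2% or 5%, independent between people. The 80% power level is this review's yardstick; the protocol calls the study a pilot and sets no target.

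**One loss.** The noncentrality is d / √(1/n₁ + 1/n₂), with n₁ + n₂ − 2 degrees of freedom.
- 15 v 15: 1.06 / √(1/15 + 1/15) = 2.903, df 28, power 80.0%.
- 14 v 15: 1.06 / √(1/14 + 1/15) = 2.852, df 27, power 78.5%.

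The difference detectable with 80% power moves from 1.06 to 1.08.

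The planned three-visit interaction F test, with sphericity assumed, gives nearly the same answer. Noncentrality 10.17 on 2 and 56 df gives 80.0%. One loss scales it by (14 × 15/29) / (15 × 15/30) = 0.9655 and leaves 2 and 54 df, which gives 78.4%.

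**Average over the possible losses.** If all 30 have TMS, expected loss is 30p and the chance of at least one loss is 1 − (1 − p)³⁰. Average power is the t-test power at d = 1.06, weighted by the binomial probability of each number of losses in each arm.

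| Assumed p | Expected loss | Chance of at least one | Same, if only 20 have TMS | Average power (30 have TMS) |
|---|---|---|---|---|
| 0.5% | 0.15 | 14% | 10% | 79.8% |
| 1% | 0.3 | 26% | 18% | 79.6% |
| 2% | 0.6 | 45% | 33% | 79.1% |
| 5% | 1.5 | 79% | 64% | 77.7% |

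The column for 20 is illustrative. Section E.1.a lets people with TMS contraindications join without that evaluation, but gives no number.

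**Effect of later randomisation.** Someone who leaves during baseline is not yet allocated and can be replaced, so this route costs no randomised person. The strata need only the initial hand scores and do not change.

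**The case against.** The strongest reply is that the protocol may already do this. The order is inferred from a list in the human-subjects section that describes what a person will undergo, and the list is not strictly chronological: item 5 counts the hand assessment of item 2 as the first evaluation. Randomising just before session 1 is compatible with the text, and in that case there is no baseline loss. This stands. The documents do not establish that allocation precedes TMS, only that its place is not fixed and that the written order puts it first.

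A reader might also infer that the protocol says nothing about when randomisation occurs. That goes too far: eligibility is the trigger, and the strata place it after the first hand assessment.

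The reach of the exit sentence is uncertain too. It is ungrammatical, and Section D's portion-only payment wording for assessments missed through safety risks points to the section that contains it. Several places also keep people who cannot have TMS in the study. These do not cancel the sentence, since Section D deals separately with stopping participation and the other places concern screening. They do mean that its effect on the hand evaluations cannot be taken as settled.

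Finally, a high chance of losing at least one person is not a large effect on the result, and the 5% rate is hard to square with a risk that Section E.1.c calls very low. Both points are fair; average power is the better summary.

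**Conclusion.** The point holds as a minor, inexpensive improvement to the design. In the written order a randomised person can be lost before therapy, with no post-baseline hand score. One loss costs about 1.5 percentage points of power (80.0% to 78.5%). Averaged over the assumed exit rates, the fall is between 0.2 and 2.3 points, and the true number lost may be zero.

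Two stronger readings are not supported. One is that such losses would bias the comparison. A loss at baseline TMS comes before any vibration, and participants are blinded, so it should not depend on the group; what remains is precision and chance imbalance. The other is that moving randomisation would deal with every exit at TMS. The exit sentence names no visit, so someone could also leave at post-therapy TMS and lose the two-week hand score. That is a separate question, which later allocation does not answer.

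The sizes rest on exit rates that the documents do not give, a two-sided 5% test, and an 80% yardstick chosen here. The case for the change does not depend on them: the allocation is first used at therapy, and nothing in the documents needs it sooner.

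**What to change.** **Timing.** State in Section D, and align Section E.1.a, that randomisation takes place after all pre-intervention evaluations that apply to the person are complete, immediately before therapy session 1, within the same Fugl-Meyer and Semmes-Weinstein strata. State that the 30 are people randomised, and that anyone who leaves during baseline is replaced before allocation. This takes a short amendment and no new procedures. The allocation must be ready at therapy visit 1, and each replacement needs a further baseline set, paid at up to 4 × $25 = $100 under Section D.

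**Reconciliation.** The investigators should reconcile three statements: the session-stop and study-stop sentences in Section E.2.b, and the portion-only wording in Section D. The text should then say whether the scheduled hand-function evaluations continue for a randomised person who stops TMS. If they do, the payment rule needs to match, because Section D ends payment for people who stop participating. This review does not say which clinical rule is right.
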